### **3.8 Sample size calculation**

Sample size was calculated in consultation with the department of Biostatistics, Seoul St. Mary's Hospital. The reference SSI rate following skin stapling in laparoscopic colorectal surgery was estimated at 5.8%, based on published literature (Lee CS et al, 2020). The non-inferiority margin was set at 0.99 percentage points (i.e., the absolute difference in SSI rate between the skin adhesive and stapling groups must not exceed 0.99% in favor of stapling for the tissue adhesive to be declared non-inferior).

Using a one-sided Z test (unpooled), one-sided alpha of 0.025, and power of 80%, the required sample size is 152 participants per group, for a total of 304 participants. No adjustment for anticipated dropout has been made because both interventions are applied at the time of surgery; however, a 10% safety margin may be considered at the interim review.

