### 3.4 Randomization

Randomization was performed using a computer-generated sequence created by the Department of Biostatistics at Seoul St. Mary's Hospital. Allocation was stratified by surgical approach (laparoscopic vs robotic-assisted) and tumor location (colon vs rectum). Within each stratum, block randomization with variable block sizes (4,6, and 8) ensured balance while minimizing predictability.

Allocation concealment was achieved through a centralized, web-based system managed by an independent biostatistician not involved in patient recruitment, enrollment, or outcomes assessment. Patients were randomized

the day before surgery in a 1:1 ratio to either the skin adhesive (Bond) or skin stapling (Stapler) group. Treatment allocation was concealed from all clinical staff until assignment.

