#### Summary Statements

Sample sizes of 152 in group one and 152 in group two achieve 80% power to detect a non-inferiority margin difference between the group proportions of 0.0099. The reference group proportion is 0.0580. The treatment group proportion is assumed to be 0.0679 under the null hypothesis of inferiority. The power was computed for the case when the actual treatment group proportion is 0.0100. The test statistic used is the one-sided Z test (unpooled). The significance level of the test was targeted at 0.0250.

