### 3.9 Statistical Analysis

All analyses will be performed using SPSS version 27.0 (IBM Corp) or R version 4.3 or later. The primary non-inferiority analysis will be conducted on both the per-protocol (PP) population and the intention-to-treat (ITT) population; non-inferiority will be claimed only if both analyses are concordant.

The primary endpoint (SSI rate) will be analyzed using a one-sided Z test for the difference in proportions, with the 95% confidence interval for the difference (skin adhesive minus stapling) reported. Non-inferiority will be concluded if the upper bound of the 95% confidence interval is below the pre-specified non-inferiority margin of 0.99 percentage points.

Continuous secondary endpoints (VAS, length of stay, operative time, cost) will be compared using the Student's t-test or Mann-Whitney U test as appropriate. Categorical variables (complication rates, patient satisfaction categories, pathological stage) will be analyzed using the chi-square test or Fisher's exact test. A two-tailed p-value of <0.05 will be considered statistically significant for all secondary comparisons.

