## 4. Study Schedule

		Study Period						
		Enrollment	Allocation	Post-allocation				Close-out
	Time point	-2 to 0 day	Operation day	Postoperative day 1	Postoperative day 2	Postoperative day 3	Discharge	First OPD f/u
Enrollment	Eligibility screen	O						
	Informed consent	O						
	Randomization		O					
	Allocation		O					
Intervention	Experimental intervention		O					
	Control intervention		O					
Assessment	Demographical data	O						
	Medical history	O						
	Laboratory	O	O		O		O	
	Parameters of surgical procedure		O					
	VAS score		O	O	O	O		
	Documentation of SSI		O	O	O	O		O
	Documentation of other complication		O	O	O	O		O
	Length of hospital stay							O
	readmission							O
	Patient questionnaire							O
	Pathologic results							O
	Cost outcomes							O

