## 5.2 Stopping Rules and Withdrawal Criteria

An individual participant will be withdrawn from the study if:

- The participant withdraws consent at any time
- The participant receives wound-healing-modifying medications (immune-suppressants or systemic corticosteroids) not present at baseline
- The participant undergoes an unplanned additional abdominal surgery within the observation period

There are no predefined stopping rules for the overall trial, as both interventions carry minimal incremental risk beyond standard care.

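### The reason given for making no dropout allowance does not hold: the stated 80% applies to 152 evaluable patients per arm in the per-protocol set, not to 304 randomised

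*Protocol*

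**What the plan says.** Section 3.8 sets 152 participants per group, 304 in total, for 80% power at one-sided alpha 0.025 with an unpooled Z test. On losses it says: "No adjustment for anticipated dropout has been made because both interventions are applied at the time of surgery". It then adds that "a 10% safety margin may be considered at the interim review".

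Other sections bear on this:

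- Section 3.4 randomises patients "the day before surgery in a 1:1 ratio". The Section 4 schedule instead marks its "Randomization" row under the operation day.
- Section 3.9 analyses the primary endpoint in both the PP and ITT populations, and "non-inferiority will be claimed only if both analyses are concordant".
- Section 5.2 withdraws a participant who withdraws consent, who receives immunosuppressants or systemic corticosteroids not present at baseline, or who has an unplanned further abdominal operation in the observation period. It also says: "There are no predefined stopping rules for the overall trial".

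No interim review is described anywhere else in the protocol.

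**The concern.** Applying the closure at surgery ensures that a patient who reaches closure receives an intervention. It does not ensure that the patient stays in the analysis. Two of the three withdrawal grounds in Section 5.2 typically arise after closure, and consent can be withdrawn at any time. With randomisation the day before, a patient can also be lost between allocation and closure. Because success needs both analysis sets, the smaller one, PP, limits the chance of success.

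Three things are at stake. A reader will take 80% as the power for 304 randomised patients, when it is the power for 152 evaluable per arm. Two sections disagree on when allocation happens, and that timing determines how many exclusions can arise after allocation in an open-label trial. The only stated contingency is tied to a review whose content, timing and access to data are not defined.

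**Working it through.** **Inputs from the protocol** (Section 3.8 and the sample-size output that follows it): stapling rate p2 = 0.058 ("The reference group proportion is 0.0580"); adhesive rate assumed for power p1 = 0.010; margin 0.0099; one-sided alpha 0.025; power 80%; unpooled Z test, normal approximation.

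**Assumption:** the protocol gives no expected loss rate. Its only figure is the optional 10%. I show 5, 10 and 15% as assumed PP losses, equal in both arms.

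**Step 1. Reproduce the plan.**

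n = [p1(1−p1) + p2(1−p2)] × (z0.975 + z0.80)² / [margin − (p1 − p2)]²

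- Variance term: 0.0099 + 0.054636 = 0.064536
- Distance: 0.0099 + 0.0480 = 0.0579
- n = 0.064536 × (1.95996 + 0.84162)² / 0.0579² = 151.1, so 152 per arm

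Power(n) = Φ(0.0579 / √(0.064536/n) − 1.95996)

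- n = 152: Φ(2.8100 − 1.9600) = 0.80233, the plan's figure exactly
- n = 151: 0.79975

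Losing one evaluable patient per arm already takes the formula below 80%.

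**Step 2. PP power by the same formula, and the number needed to keep 152 evaluable** (152/(1 − loss), rounded up).

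| Assumed PP loss | Evaluable per arm | PP power | Randomised per arm to keep 152 | Total |
|---|---|---|---|---|
| 0% | 152 | 80.2% | 152 | 304 |
| 5% | 144.4 | 78.2% | 160 | 320 |
| 10% | 136.8 | 76.0% | 169 | 338 |
| 15% | 129.2 | 73.6% | 179 | 358 |

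The probability that both analyses succeed cannot exceed the PP probability.

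**Step 3. Check against the rule that will be applied.** Section 3.9 concludes non-inferiority if the upper 95% limit for the difference is below the margin. With the unpooled Z test of Section 3.8, that is the Wald interval. The normal approximation understates the power of this rule at these rates: exact binomial enumeration gives 87.3% at 152 per arm, not 80.2%. I simulated joint ITT-and-PP success with ITT complete at 152 per arm and PP losses unrelated to outcome. The ranges reflect whether the loss is a fixed or a random number.

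| Assumed PP loss | Joint power, Wald rule |
|---|---|
| 0% | about 87% |
| 5% | about 83 to 84% |
| 10% | about 80.5 to 81% |
| 15% | about 76 to 77% |

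**Step 4. Timing, side by side.** Section 3.4 places randomisation the day before surgery. Section 4 places both randomisation and allocation on the operation day, with enrolment and consent in the column for days −2 to 0. Both cannot be right.

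**The case against.** The strongest reply is that the 304 patients may well deliver 80% under the analysis actually planned. Step 3 supports this up to about 10% loss. A reader might infer that the trial is underpowered because of dropout. The documents do not support that: the shortfall is firm only against the plan's own normal-approximation formula, and the loss rates are assumptions.

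Other stronger readings also fall short:

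- **Consent after randomisation.** Consent up to day 0 beside randomisation on day −1 might suggest this. Section 3.2.1 requires written consent before enrolment, and the schedule puts consent in the column before allocation. Only the mismatch in the randomisation day remains.
- **Conversions and findings in theatre as PP losses.** Section 3.2.1 asks only that a minimally invasive resection be scheduled. The protocol does not say how conversions, cancellations or multi-organ resections found at surgery are handled. The definition of the PP set may properly sit in the statistical analysis plan.
- **Inflated error from a top-up.** Nothing says that the interim review would see infection rates by arm, and Section 3.5 keeps the statistical analysis blind to group until completion. The risk is conditional. What stands is that the review is undefined.
- **Attrition up to day 30.** Section 3.6.1 sets a 30-day window, but Section 2.1 says the endpoint is assessed at discharge. How much late attrition applies cannot be settled from the text, so I do not rely on it.

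None of this rescues the stated reason. Section 5.2 alone contradicts it.

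**Conclusion.** The point holds, with modest size. The reason for making no allowance is inconsistent with Sections 3.4, 3.9 and 5.2, and that conclusion needs no assumed loss rate. Against the plan's own formula, power falls by about 2 points at 5% PP loss, 4 at 10% and 7 at 15%. Under the planned interval rule, joint power drops below 80% only once loss passes about 10%. These figures assume equal losses in the two arms. The simulated ones also assume that losses are unrelated to outcome and that ITT is complete.

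The sample-size arithmetic itself is correct. All these power figures rest on the assumed 1.0% adhesive rate, which matters far more than dropout: with 5.8% in both arms, the same formula gives about 5.6% power at 152 per arm. That is a separate issue, and a dropout allowance would not address it.

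The conflict over the randomisation day and the undefined interim review should be corrected whatever the power.

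**What to change.** 1. **Section 3.8.** Delete the reason for making no allowance. State that 304 patients are randomised, that the 80% applies to 152 evaluable per arm, and that by the same formula power is about 76% with 10% PP loss. This discloses the shortfall and does not remove it. Holding 152 evaluable at 10% loss would need 338 randomised.
2. **Section 3.4 and the Section 4 schedule.** Give one randomisation day in both places, with consent always before randomisation. Randomise as late as is practical, for example through the existing web system once eligibility is confirmed, to limit exclusions after allocation. Later randomisation is an optional design change and would not prevent the withdrawals in Section 5.2.
3. **Interim-review clause.** Delete it, or limit it to a check of the pooled non-evaluable fraction with no infection data by arm.

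The cost is protocol wording, a slightly less favourable power statement and, if randomisation is moved, a change to the allocation workflow. No extra patients are needed. Section 3.4 is written in the past tense; if allocation has already taken place, item 2 reduces to describing the timing as it happened.

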### Analysis of Non-Inferiority Tests of Two Independent Proportions

#### Numeric Results for Non-Inferiority Tests Based on the Difference: P1 - P2

H0: P1 - P2 ≥ D0. H1: P1 - P2 = D1 < D0. Test Statistic: Z test (unpooled)

Target Diff Power Alpha	Actual Diff Power	Target N1	N2	N	Ref. P2	P1 H0 P1.0	P1 H1 P1.1	NI D0	D1
0.80 0.0480	0.80233 0.0250	152	152	304	0.0580	0.0679	0.0100	0.0099	-

Note: Direct Binomial distribution calculations for alpha and power were only used when both N1 and N2 were less than 100. In all other cases, Normal approximation was used.

#### Report Definitions

Target Power is the desired power value (or values) entered in the procedure. Power is the probability of rejecting a false null hypothesis.

Actual Power is the power obtained in this scenario. Because N1 and N2 are discrete, this value is often (slightly) larger than the target power.

N1 and N2 are the number of items sampled from each population.

N is the total sample size, N1 + N2.

P2 is the proportion for Group 2. This is the standard, reference, or control group.

P1 is the treatment or experimental group proportion. P1.0 is the largest treatment-group response rate that still yields a non-inferiority conclusion. P1.1 is the proportion for Group 1 at which power and sample size calculations are made.

D0 is the non-inferiority margin. It is the difference P1 - P2 assuming H0. D1 is the difference P1 - P2 assumed for power and sample size calculations.

Target Alpha is the input probability of rejecting a true null hypothesis. Actual Alpha is the value of alpha that is actually achieved.

#### Summary Statements

Sample sizes of 152 in group one and 152 in group two achieve 80% power to detect a non-inferiority margin difference between the group proportions of 0.0099. The reference group proportion is 0.0580. The treatment group proportion is assumed to be 0.0679 under the null hypothesis of inferiority. The power was computed for the case when the actual treatment group proportion is 0.0100. The test statistic used is the one-sided Z test (unpooled). The significance level of the test was targeted at 0.0250.

### 3.9 Statistical Analysis

All analyses will be performed using SPSS version 27.0 (IBM Corp) or R version 4.3 or later. The primary non-inferiority analysis will be conducted on both the per-protocol (PP) population and the intention-to-treat (ITT) population; non-inferiority will be claimed only if both analyses are concordant.

The primary endpoint (SSI rate) will be analyzed using a one-sided Z test for the difference in proportions, with the 95% confidence interval for the difference (skin adhesive minus stapling) reported. Non-inferiority will be concluded if the upper bound of the 95% confidence interval is below the pre-specified non-inferiority margin of 0.99 percentage points.

Continuous secondary endpoints (VAS, length of stay, operative time, cost) will be compared using the Student's t-test or Mann-Whitney U test as appropriate. Categorical variables (complication rates, patient satisfaction categories, pathological stage) will be analyzed using the chi-square test or Fisher's exact test. A two-tailed p-value of <0.05 will be considered statistically significant for all secondary comparisons.

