### **3.7. Data Collection**

Baseline variables will be collected preoperatively and include: age, sex, body mass index (BMI), ASA class, diabetes mellitus status, smoking history, prior abdominal surgery, preoperative serum white blood cell count (WBC), and C-reactive protein (CRP). Intraoperative data will include operative technique, type of resection, specimen extraction incision length, operative time, and estimated blood loss. Postoperative data will include histopathological results (tumor type, TNM stage), SSI occurrence, VAS pain scores, length of stay, complications, wound care resource utilization, and patient-reported satisfaction.

All data will be recorded on standardized case report forms (CRFs) and entered into a password-protected electronic database. Source data verification will be performed quarterly by the principle investigator.

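### Section 3.9 fixes unadjusted two-sample tests for operative time and length of stay, giving up precision that the stratification factors and preoperative covariates could supply at no data cost

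*Protocol*

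**What the plan says.** Section 3.9 names the analysis of the continuous secondary endpoints: "Continuous secondary endpoints (VAS, length of stay, operative time, cost) will be compared using the Student's t-test or Mann-Whitney U test as appropriate". It mentions neither covariates nor stratification factors.

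Section 3.4 describes the design that produces the data: "Allocation was stratified by surgical approach (laparoscopic vs robotic-assisted) and tumor location (colon vs rectum", with 1:1 assignment before surgery.

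Section 3.7 lists what is known about each patient before the operation: "Baseline variables will be collected preoperatively and include: age, sex, body mass index (BMI), ASA class, diabetes mellitus status, smoking history, prior abdominal surgery", followed by two laboratory values. It does not say that any of these will be used for adjustment.

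For categorical variables, section 3.9 says: "Categorical variables (complication rates, patient satisfaction categories, pathological stage) will be analyzed using the chi-square test or Fisher's exact test". The next sentence sets the threshold: "A two-tailed p-value of <0.05 will be considered statistically significant for all secondary comparisons". Stage is not in the secondary endpoint table of section 3.6.2; section 3.7 records it among the findings on the specimen: "Postoperative data will include histopathological results (tumor type, TNM stage".

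**The concern.** Operative time is defined in section 3.6.2 as running from incision to wound closure. Skin closure is only its last step, so the variation from the resection that precedes it is noise for the comparison of closure methods. Length of stay likewise depends on much besides the wound. Age, BMI, ASA class, prior abdominal surgery, surgical approach and tumour location are plausible sources of that variation, and all are known before closure. A two-sample test leaves their contribution in the error term. At stake are wider intervals and lower power for two listed secondary endpoints.

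The stratification factors add a second aspect. Stratified blocks balance the arms on these factors and so reduce the true variability of the arm difference. A t-test that ignores the strata still estimates its standard error as if that balance had not been imposed.

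A smaller matter is the test of pathological stage. Stage is a property of the tumour, and patients are randomised to a method of skin closure. A p-value for stage therefore says nothing about closure.

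**Working it through.** **1. The plan's own figure.** The only power calculation in the protocol is for SSI (section 3.8). With rates 0.058 and 0.010, margin 0.0099, one-sided alpha 0.025 and power 80%:

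- n = (1.96 + 0.8416)² × (0.058 × 0.942 + 0.010 × 0.990) / (0.048 + 0.0099)² = 7.849 × 0.064536 / 0.003352 = 151.1, rounded up to 152 per group.
- Power at 152 = Φ(0.0579 / √(0.064536/152) − 1.96) = 0.8023, matching the stated 0.80233.

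This point does not affect that figure. It supplies the 152 per arm used below.

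**2. Reference effect for a continuous endpoint.** The protocol gives no SD, target difference or power for operative time or length of stay. The difference at which an unadjusted two-sided 5% test has 80% power is (1.96 + 0.8416) × √(2/152) = 0.321 SD. It is a reference point, not a planning value of the trial.

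**3. Gain from covariates not used in stratification.** If covariates explain a share R2 of the outcome variance, the standard error of the arm difference is multiplied by √(1 − R2), and power at the same difference is Φ(2.8016/√(1 − R2) − 1.96). R2 is assumed:

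| R2 | SE factor | SE reduction | Power | Equivalent unadjusted n per arm, 152/(1 − R2) |
|---|---|---|---|---|
| 0 | 1.000 | – | 0.80 | 152 |
| 0.05 | 0.975 | 2.5% | 0.82 | 160 |
| 0.10 | 0.949 | 5.1% | 0.84 | 169 |
| 0.20 | 0.894 | 10.6% | 0.88 | 190 |
| 0.30 | 0.837 | 16.3% | 0.92 | 217 |

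A simulation with 3,000 runs per scenario agrees. At R2 = 0.10, power was 0.81 unadjusted and 0.84 adjusted; at 0.30 it was 0.81 and 0.92. Under no effect, the unadjusted t-test rejected in 4.7% to 5.6% of runs over R2 = 0.10 to 0.50, so it is valid.

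**4. Stratification factors.** With balance within strata, the true standard error is √(1 − R2) times the one the t-test uses. Its actual two-sided error rate is then about 2 × [1 − Φ(1.96/√(1 − R2))]:

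- R2 = 0.10: 2 × [1 − Φ(2.066)] = 0.039 (simulated 0.038).
- R2 = 0.30: 2 × [1 − Φ(2.343)] = 0.019 (simulated 0.020).

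The simulation used four equally likely strata, balanced to within one patient. With adjustment, the simulated error rate was 0.047 and 0.046. Power at 0.321 SD went from 0.82 to 0.84 at R2 = 0.10 and from 0.83 to 0.91 at R2 = 0.30. The gain is a little smaller than in step 3 because stratification has already secured part of the power.

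**5. Why the primary analysis is different.** Expected SSI events under the design rates are 152 × (0.058 + 0.010) = 10.3. That is too few to support several patient-level covariates.

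**6. Stage.** Under randomisation, any difference in stage between arms is chance. A test at 0.05 flags one at most about 5% of the time, and the result informs no endpoint.

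**The case against.** The strongest reply is that nothing here is an error. A t-test or Mann-Whitney test is valid in a 1:1 randomised comparison, collecting baseline data does not commit a trial to adjusting for them, and adjustment of secondary endpoints is often left to the SAP, which is not at hand. Most of this stands: the tests are valid and no passage contradicts another. But section 3.9 is not silent. It names the tests for these endpoints, so an adjusted analysis would have to replace a stated choice.

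It can also be said that the size is unanchored, and that stands too. The protocol gives no R2 or SD and does not say that these covariates predict the outcomes. At R2 = 5%, power moves only from 80% to 82%. The protocol also gives no data on the shape of the two distributions, so it does not support insisting on a log scale with a ratio as the effect measure.

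A reader might infer that the protocol treats stage as something closure could change. The text does not support this. Section 3.9 calls stage a categorical variable, and neither the objectives (2.2) nor the endpoint table (3.6.2) lists it. It may be meant as a check that the arms are comparable. Such a test is uninformative under randomisation as well, but it feeds no decision.

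**Conclusion.** The point holds as a free improvement to two secondary endpoints, not as a flaw that invalidates an analysis. For an assumed R2 of 5% to 30%, adjustment would cut standard errors by 2.5% to 16% and raise power from 80% to between 82% and 92% at 0.32 SD with 152 per arm. These figures assume a linear model with complete data, and the R2 range and reference effect are not from the protocol. If surgical approach and tumour location are prognostic, the unadjusted t-test is also conservative.

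A reader might infer that the unadjusted comparisons are biased or produce too many false positives. They do not: the simulated error rate is close to 5% for covariates outside the stratification, and below 5% when a prognostic stratification factor is ignored. The SSI conclusion and the 304 patients are unaffected. The test of stage is a minor matter of presentation.

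**What to change.** - **Operative time and length of stay (3.9).** Replace the two-sample tests with a pre-specified linear model for arm, adjusted for surgical approach and tumour location as used in randomisation, and for age, BMI, ASA class and prior abdominal surgery. Fix the scale, raw or log, before by-arm data are seen. Report the adjusted difference (raw scale) or ratio (log scale) with its 95% interval.
- **Primary SSI analysis.** Leave it without these patient-level covariates.
- **Pathological stage.** Remove it from the list of tested variables and report it by arm as counts and percentages, without a p-value.

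The cost is wording in the protocol or SAP. No new data, visits or patients are needed. The one constraint is timing: covariates and scale must be settled before anyone sees outcomes by arm.

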### 2.2 Secondary objective

To compare postoperative pain intensity (VAS score, 0-10) at postoperative days 1 and 3.

To compare length of hospital stay.

To compare the incidence of major postoperative complications within 30 days

To compare total operative times (minutes).

To compare total wound-related cost-effectiveness between the two groups, including device cost and wound dressing service cost.

To assess wound healing quality and patient satisfaction via a validated questionnaire administered at the outpatient clinic visit one week after discharge.

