#### **3.6.2 Secondary Endpoints**

Outcomes	Measurement Tool	Time point
Pain score	Visual Analogue Scale (VAS, 0-10)	POD1, 2, and 3
Length of hospital stay	Day from surgery to discharge	At discharge
Operative time	Minutes (skin incision to wound closure)	Intraoperative
Major complications	Clavien-Dindo classification	Within 30 days
Cost effectiveness	Dressing supply cost, dressing service cost, Dressing frequency	Until discharge
Patient satisfaction and wound quality	Validated wound questionnaire, investigator wound assessment	1 week postop discharge OPD visit

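### Section 3.9 lets cost be compared by Mann-Whitney, which does not address mean wound-related cost and can point the wrong way if adhesive is routinely dearer and one SSI costs more than about 20.8 times that premium

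*Protocol*

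**What the plan says.** Protocol Section 3.9 groups cost with pain score, length of stay and operative time: "Continuous secondary endpoints (VAS, length of stay, operative time, cost) will be compared using the" one of two tests. All four "will be compared using the Student's t-test or Mann-Whitney U test as appropriate". No rule for choosing between the tests is attached, and nothing ties the cost comparison to the mean. The significance rule is common to all of them: "A two-tailed p-value of <0.05 will be considered statistically significant for all secondary comparisons".

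The objective behind the cost endpoint, in Section 2.2, is "To compare total wound-related cost-effectiveness between the two groups, including device cost and wound dressing service cost". The endpoint table in Section 3.6.2 describes the same endpoint more narrowly, as "Dressing supply cost, dressing service cost, Dressing frequency", counted until discharge and without the device.

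The planning SSI rates come from the summary of the sample size calculation: "The reference group proportion is 0.0580" for stapling and, for adhesive, "The power was computed for the case when the actual treatment group proportion is 0.0100".

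**The concern.** Total wound-related cost in an arm is the number of patients times the arithmetic mean, so a comparison of total cost is a comparison of means. Mann-Whitney compares ranks. It asks whether a patient in one arm tends to cost more than a patient in the other, and an infected wound counts only as one more high rank, however expensive it is.

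If most patients have a modest routine cost and a few with SSI have a large one, the data are skewed, and many analysts would read the instruction in Section 3.9 as a reason to use Mann-Whitney. The cost result would then rest almost wholly on the routine patients. A named secondary objective could be reported with a significant difference when mean costs are equal, or with a difference in the opposite direction to the means. Even without a reversal, a rank test gives no mean cost difference with an interval.

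**Working it through.** **Inputs from the protocol.** SSI 5.8% (stapling) and 1.0% (adhesive); 152 patients per arm; one-sided alpha 0.025; secondary tests two-sided at 0.05. "The non-inferiority margin was set at 0.99 percentage points". Adhesive wounds get no additional dressing and stapled wounds get standard dressings (Sections 3.3.1 and 3.3.2).

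**Assumptions, because the protocol gives no unit costs.** d is the extra routine cost of adhesive over stapling, device included. S is the extra cost of one SSI. CV is the coefficient of variation of routine cost.

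**1. The plan's own figure.** The standard error is √[(0.058 × 0.942 + 0.010 × 0.990)/152] = 0.0206. Power = Φ[(0.0099 + 0.048)/0.0206 − 1.96] = 0.802. This agrees with the stated 152 per group and power of 0.80233, so these are the rates the plan uses.

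**2. What the mean sees.** Mean difference (adhesive minus stapling) = d − (0.058 − 0.010) × S = d − 0.048 × S. Adhesive is cheaper on average when S > d/0.048 = 20.8 × d.

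**3. What the ranks see.** Expected SSIs are 152 × 0.058 = 8.8 (stapling) and 152 × 0.010 = 1.5 (adhesive). With no spread in routine cost, d > 0 and S > d, adhesive ranks above stapling in 0.942 + 0.058 × 0.010 = 94.3% of patient pairs, however large S is. Ranks follow the sign of d; the mean follows d − 0.048 × S. They disagree when 0 < d < 0.048 × S.

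**4. Illustration.** 152 per arm, stapling routine cost 100, d = +10, every SSI costed. The true mean difference is 10 − 0.048 × 300 = −4.4 for S = 300 and 10 − 0.048 × 500 = −14 for S = 500, so adhesive is cheaper in both.

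| CV of routine cost | Mann-Whitney significantly favours stapling |
|---|---|
| 10% | about 100% of trials |
| 20% | about 87% |
| 30% | about 45% |
| 50% | about 15% |

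At CV 20% and S = 500, Mann-Whitney favours adhesive in 0% of trials. The t-test favours stapling in 0.1% and adhesive in 17%. With a smaller premium (d = +5, S = 500, CV 20%), the Mann-Whitney reversal falls to 21%.

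**5. When adhesive is not routinely dearer.** With d = −10, CV 20% and S = 500, Mann-Whitney favours stapling in 0% of trials and adhesive in 99.9%. With d = 0 it favours stapling in about 0.5%. There is essentially no reversal.

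**6. A model in units of one dressing change.** Assume on average three routine dressings per stapled patient, none with adhesive, and a device premium for adhesive.
- Premium 3.5, S = 20: mean difference 3.5 − 3 − 0.048 × 20 = −0.46; Mann-Whitney favours stapling in 91%.
- Premium 4.5, S = 50: mean difference 4.5 − 3 − 0.048 × 50 = −0.90; Mann-Whitney favours stapling in 100%.
- Premium 0 or 2.5 (adhesive routinely cheaper): ranks and means both favour adhesive.

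**7. The cost window.** SSI is counted to 30 days but cost only until discharge. If half of SSIs fall before discharge (assumed for both arms), 0.048 becomes 0.024 and the threshold becomes d/0.024 = 41.7 × d. In the illustration, S = 300 then gives 10 − 7.2 = +2.8, so stapling really is cheaper and the rank test has the right direction. S = 500 gives 10 − 12 = −2.0, a small reversal.

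**The case against.** A reader might infer that the planned SSI rates by themselves make the cost analysis name the wrong closure. The documents do not support that. Reversal also needs adhesive to be dearer in the routine patient and an SSI to cost more than about 20.8 times the premium, and the protocol states neither. What it does say about routine dressing cost points the other way: dressings are used only with stapling, and the Background cites retrospective data suggesting lower wound care costs with adhesive. On the dressing components in Section 3.6.2 alone, adhesive would be routinely cheaper and the two measures would agree in direction. Reversal needs the Section 2.2 definition, with a net device premium larger than the dressing saving.

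A reader might also infer that Mann-Whitney will be used. Section 3.9 names no normality rule and allows Student's t-test, which does compare means and, with equal arms, behaves much like Welch's test. Nor can it be assumed that every 30-day SSI enters the cost endpoint, since the window closes at discharge.

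It can be said, too, that the choice of test per endpoint is detail for an analysis plan that is not shown. This last argument has limited force. Section 3.9 does not leave cost open: it names cost and permits a test that does not target the quantity in the objective. The other objections stand, and they limit the size of the point without removing it.

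**Conclusion.** The point holds in a conditional form. Section 3.9 permits, for cost, a test that does not address the difference in mean wound-related cost and gives SSI patients almost no weight. A significant result in the wrong direction is possible when 0 < d < 0.048 × S, with a stricter condition if only SSIs before discharge are costed.

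The 15% to 100% in the illustration rests wholly on assumed costs (d = +10 on a base of 100, S of 300 to 500, all SSIs costed) and on SSI rates of 5.8% and 1.0%. How likely those conditions are cannot be judged from the protocol. If adhesive is routinely cheaper, the direction is safe, but a rank test still does not estimate the mean cost difference. The endpoint is secondary, and the primary non-inferiority conclusion is unaffected.

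**What to change.** Take cost out of the shared sentence in Section 3.9. State that total wound-related cost per patient will be analysed as the difference in arithmetic means, adhesive minus stapling, with a bootstrap or Welch 95% confidence interval whatever the skew. Medians or a rank test may be given as description only. Sections 2.2 and 3.6.2 should be reconciled on whether device cost is included, because the sign of d depends on it.

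The change of analysis costs one sentence and a few lines of code, with no change in sample size. The downside is that the interval may look less decisive than a rank-test p-value: in the illustration at CV 20% and S = 500, the t-test on means detected adhesive's lower cost in only 17% of trials.
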